7 SUBJECT CONFIDENTIALITY

Participant confidentiality will be maintained during and after the interview in several ways:

- The interview will be conducted in a private place where the interview cannot be overheard.
- Interviewers will be trained in research integrity and ethics, including protecting participant information.
- Informed consent will be conducted verbally, thereby reducing the risk of a breach of client confidentiality by eliminating any paper record of clients' participation in the study with signature.
- Data will be collected on tablets which will be encrypted and password protected.
- Individuals will be assigned a unique study ID. No information that could be used to identify the participant will be recorded such as names, identification numbers, dates of birth or address.
- Anyone older than 80 years of age will be recorded as '80.'
- Data will be transferred from the tablet to a secure, password protected computer once per week.
- Data will be stored on an encrypted, password protected computer and backed up on Duke Box. The data will only be accessible to the Data Manager and the PI. It will be reviewed regularly to ensure quality and completeness.
- Only fully de-identified data will be provided to other study personnel or statisticians. Only fully de-identified data will be shared.

7.1 Future Use of Stored Specimens

Not applicable.

8 INFORMED CONSENT PROCESS

Pharmacies will be approached and the study described. If they agree to participate, they will be asked to consent to a baseline survey that collects details about the outlet (Appendix 4,5). This will be conducted in a private area and at a time that is convenient for their business.

Informed consent will be obtained prior to collecting any participant information for research purposes. Clients will be approached as they leave the pharmacy and asked if they would be willing to participate in a brief interview. If so, the interviewer will conduct screening and consent in a private area away from other clients. The client will be given time to ask questions and will be asked to give verbal consent for the interview, which will be documented by the interviewer. The interviewer will explain the purpose of the study, the risks, benefits, and safeguards in place to protect the participant's information. A printed copy of the consent script will be available for them to read and to keep. Contact information for the Study Coordinator or PI will be provided so the participant can ask questions after the interview.

No individual identifying information will be collected during the interview, therefore withdrawing consent after the interview is closed will not be possible. To mitigate this, the interviewer will confirm consent by asking at the end of the survey if the participant is comfortable with all the answers and agrees for their information to be retained.

8.1 Informed Consent/Assent Process (in Case of a Minor or Others Unable to Consent for Themselves)

The study will only enroll minor participants present with a parent or guardian and all questions will be directed to the parent/guardian. Therefore, we do not anticipate interacting with minors or needing assent from the minor.

We will not enroll individuals who are unable to consent for themselves such as those who are mentally impaired or are experiencing impaired consciousness.

9 RESULT DISSEMINATION PLAN

The results from this trial will be disseminated to the county and sub-county health teams, National Malaria Control Program, and the Director of Medical Services through meetings and a policy brief.

We shall also support the sub-county health teams to disseminate the results at the community level through barazas or CHWs depending on plans for scale-up coming from national partners.

Appendix A.1

Aim 2: TESTsmART Participant exit interview

SCREENING QUESTIONS

Number	QUESTION	RESPONSE	SKIP
0.01	Did the person meet all of the inclusion criteria?	1. Yes 2. No	If yes, skip to 0.03
0.02	If no, why were they excluded from participating in the study today? (select all that apply)	1. Person did not have a fever or malaria-like illness 2. Patient with malaria-like symptoms not present 3. Patient younger than 1 year of age 4. Had symptoms of severe malaria and referred for care 5. Took antimalarial in the last seven days for current illness 6. No parent or guardian present	STOP
0.03	Did the person consent to participate in the study?	1. Yes 2. No	If No, STOP

GENERAL STUDY INFORMATION

Number	QUESTION	RESPONSE	SKIP
0.1	Date	MM/YYYY	
0.2	Participant ID		
0.3	Outlet ID		
0.4	Interviewer ID		
0.5	Language of interview	1. English 2. Swahili 3. Bokusu 4. Other	

SECTION 1: RESPONDENT INFORMATION

Number	QUESTION	RESPONSE	SKIP
1.1	Who is the respondent?	Adult with fever.....1 Guardian of the child.....2	→Q1.5
1.2	What is your relationship with the child?	Parent.....1 Grandmother/grandfather.....2 Brother/Sister.....3 Uncle/Aunt.....4 Other.....5 Specify:	
1.3	Gender of the child	Female.....1 Male.....0	
1.4	How old is the child?	— — . — years	
1.5	Gender of the respondent	Female.....1 Male.....0	
1.6	How old are you? [In the case the child is ill, please collect this information for the parent/guardian of the child]	— — years	

SECTION 2: CURRENT ILLNESS

Number	QUESTION	RESPONSE	SKIP
2.1	Which symptoms do you/your child have or had in the last 24 hours? [Mark all that apply]	1. Fever 2. Nausea 3. Headache 4. Body aches 5. Vomiting 6. Shivering 7. Stomach ache 8. Other _____ 99. Don't know	

2.2	How serious is this illness in your opinion? [Guardian of the child can guess how the child feels]	1. Not very serious/minor 2. Moderate 3. Very serious	
2.3	How many days ago did the symptoms start?	_____ days	99=Don't know
2.4	How likely is that the illness that you/your child have today is malaria?	1. Not possible 2. Unlikely but not impossible 3. 50/50 4. Likely 5. Absolutely sure 99. Don't know	
2.5	Have you sought treatment or care elsewhere for this illness?	1. Yes 2. No 99. Don't know	If no or don't know, go to 3.1
2.6	What did you do? Check all that apply	1. Visit hospital 2. Visit government health center/dispensary 3. Visit private clinic 4. Visit private laboratory 5. Visit pharmacy/chemist 6. Buy medicine at general shop 7. Gave medicine available at home 8. Visit traditional healers 9. Visit religious/cultural healers 10. Visit CHW 11. Other _____ 99. Don't know (i.e., another caregiver was involved)	
2.7	Why did you come to this facility?	1. Treatment was not available in other facilities 2. RDT tests were not available in other facilities 3. It's the closest chemist shop to me 4. This chemist shop has better prices 5. I was referred here for treatment 6. OTHER 99. Don't know (i.e., another caregiver was involved)	

2.8	Did you have a malaria test from another provider/facility/lab before coming here today?	1. Microscopy 2. RDT 3. Don't know 4. No test	If 4, go to 3.1
2.9	Malaria test results from elsewhere	1. Negative – report observed 2. Positive – report observed 3. Reported negative by respondent 4. Report positive by respondent 5. Doesn't recall result	
2.10	Do you have a copy of the test result?	1. No, nothing written 2. Yes	
2.11	How likely is it that the result of that test was correct? Only if tested elsewhere before coming to the shop today	1. Not possible 2. Unlikely but not impossible 3. 50/50 4. Likely 5. Absolutely sure Don't know	
2.12	Have you taken/given to the child any medication for this illness since it started?	1. Yes 2. No 99. Don't know	If 1, go to 2.12 If 2 or 99, go to Section 3
2.13	If so, which medicines (select all that apply)	1. AL (Lonart/CoArtem/Artefan) 2. Other ACT (DHAP, DP, Duocotexin, P-alaxin) 3. Monotherapy (Artesunate, Quinine, Chloroquine, SP/Fansidar) 4. Antibiotic (Amoxyl/Ceptrin, Metronidazole/Flagyl/Ampicillin) 5. Painkiller/fever medecine (Panadol/Brufen/Hedex/Action/Maramoja) 6. Cough medicine or decongestant 7. Other _____ 99. Don't know	If 1, 2 or 3 STOP
2.14	Did you come to the pharmacy today with a prescription from another provider/facility/lab?	1. Yes 2. No	If 2 skip to Section 3.
2.15	If yes, what was the prescription for?	1. AL (Lonart/CoArtem/Artefan) 2. Other ACT (DHAP, DP, Duocotexin, P-alaxin)	

		
3. Monotherapy (Artesunate, Quinine, Chloroquine, SP/Fansidar)
 
4. Antibiotic (Amoxyl/Ceptrin, Metronidazole/Flagyl/Ampicillin)
 
5. Painkiller/fever medecine (Panadol/Brufen/Hedex/Action/Maramoja)
 
6. Cough medicine or decongestant
 
7. Other _____
 
99. Don't know
	
2.16	Did the client show documentation of the prescription?	
1. No
 
2. Yes, a written prescription from the provider/facility/lab
 
3. Yes, other (Specify: _____)
	

Section 3: Test at Shop

Number	QUESTION	RESPONSE	SKIP
3.1	Did you (or your child) have your blood tested for malaria today at the shop?	
1. Yes
 
2. No
	If yes skip to 3.3
3.2	Why not? (Mark all that apply)	
1. Too expensive
 
2. RDT was not offered
 
3. RDT not in stock
 
4. No time
 
5. Already sure illness is malaria
 
6. Already sure illness is not malaria
 
7. Don't want to get finger pricked
 
8. Was tested elsewhere before coming
 
9. Had a prescription for drug I needed before coming
 
99. Other Specify: _____
	Next skip to section 4
3.3	RDT results from shop (self-report)	
1. Negative
 
2. Positive
 
3. Invalid
	
3.4	How likely is it that the result of the test was correct? Only if tested	
1. Not possible
 
2. Unlikely but not impossible
 
3. 50/50
 
4. Likely
	

		5. Absolutely sure Don't know	
--	--	----------------------------------	--

Section 4: Purchase Questions

Number	QUESTION	RESPONSE	SKIP
4.1	Which medicine(s) did you obtain from the shop today to treat your/your child's illness Choose all that apply,	
 1. AL (Lonart/CoArtem/Artefan) 2. Other ACT (DHAP, DP, Duocotexin, P-alaxin) 3. Other antimalarial (Artesunate injection, Quinine, Chloroquine, SP/Fansidar) 4. Antibiotic (Amoxyl/Ceptrin, Metronidazole/Flagyl/Ampicillin) 5. Painkiller/fever medicine (Panadol/Brufen/Hedex/ Action/Maramoja) 6. Cough medicine or decongestant 7. Other _____ 8. None 
99. Don't know
	If 2, 3, 4, 5, 6, 7 or 99 Skip to 4.4 If 8, skip to 5.1
4.2	How much did you pay today for the ACT? (The amount refers to how much money respondent paid for the ACT. Don't add the amount of the voucher if any was used-the amount should be between 0-5000, or 9999 for don't know)	ACT= _____ KES OR Don't know/remember...9999	
4.3	How much did you spend at the pharmacy today? (Total cost to client including RDT, ACT and any other drugs)	_____ KES	
4.4	Was there any discount for your ACT at the shop today?	
 1. Yes 2. No 3. Don't know 	

4.5	I would like to record information about each drug you purchased today. May I see the packaging?	1. Type _____ 2. Brand Name _____ 3. Price _____ KES 4. Did participant show you the drug? 1. Yes 2. No	Repeat for every drug purchased for illness
-----	---	---	---

Section 5: Household Characteristics

Number	QUESTION	RESPONSE	SKIP
5.1	What is the main source of drinking water for your household?	1. Piped water/Public Tap/borehole 2. Unprotected well 3. Protected well 4. Protected Spring 5. Unprotected Spring 6. Surface water (river, dam, lake, pond, stream, canal, irrigation channel) 7. Rain water 8. Bottled water 9. Other	
5.2	Does your household have the following items:		
a)	Electricity?	1. Yes 2. No 99. Don't know	
b)	A television?	1. Yes 2. No 99. Don't know	
c)	A refrigerator?	1. Yes 2. No 99. Don't know	
d)	A radio?	1. Yes 2. No 99. Don't know	
e)	A mobile phone (at least one member of the household has)?	1. Yes 2. No 99. Don't know	

f)	A motorcycle (at least one member of the household has)?	1. Yes 2. No 99. Don't know	
g)	A car/truck?	1. Yes 2. No 99. Don't know	
h)	A bank account (at least one member of the household has)?	1. Yes 2. No 99. Don't know	
5.3	How many of the following livestock does your household have?	1. None 99. Don't know	
a)	Cows		
b)	Sheep		
c)	Goats		
d)	Pigs		
5.4	What kind of toilet does your household have?	2. Flush or pour flush toilet 3. VIP / Ventilated improved pit latrine 4. Pit latrine with slab 5. Pit latrine without slab 6. Composting toilet 7. Bucket toilet 8. No facility / bush / field 9. Other (Please specify): _____	
5.5	What type of fuel does your household mainly use for cooking?	1. Liquefied petroleum gas 2. Paraffin/Kerosene 3. Charcoal 4. Firewood 5. Dung 6. Biogas 7. Crop residue 8. Other (Specify) _____	
5.6	Do you/your family own the house you live in?	1. Own the house 2. Rent the house	

5.7	What is the main material of the floor in your house?	3. Earthen 4. Cement 5. Floor Tiles 6. Wood planks 7. Polished wood 8. Other (please specify) <hr/>	
5.8	What is the main material of the walls in your house?	1. Stone 2. Brick 3. Timber 4. Iron Sheet 5. Mud 6. Wood 7. Cement 8. Other (please specify) <hr/>	
5.9	What is the main material of the roof of your house?	1. Iron sheets 2. Roof tiles 3. Grass Thatched 4. Wood 5. Other (please specify) <hr/>	
5.10	How many acres/hectares/feet of land for farming does your household own?	1. None 0 2. Acres _____ 3. Square Feet (xx by xx) _____ 9999. Don't know	
5.11	What is the highest level of schooling you completed? [In the case the child is ill, please collect this information for the parent/guardian of the child]	1. None 2. Primary 3. Secondary 4. College 5. University	
5.12	What is your primary occupation? [In the case the child is ill, please collect this information for the parent/guardian of the child]	Agriculture 1. Farming/Livestock keeping Paid employee 2. Government or parastatal 3. Private(specify:) 4. Self-employed With employees 5. Without employees (e.g. motorcycle taxi, vendor)	

		
6. Unpaid family helper in a business
 
Other (Not in agriculture)
 
7. Casual worker/day laborer
 
8. House help
 
9. Homemaker
 
10. Student
 
11. Not available to work
 
12. Other (Specify) _____
	
--	--	--	--

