6 STATISTICAL CONSIDERATIONS

6.1 Study Outcome Measures

The primary outcome measure is the proportion of all ACTs that are sold to individuals with a positive malaria diagnostic test defined as anyone who is tested at the outlet and receives a positive test result or is referred from a health facility with a documented positive test result.

Among secondary outcomes, behavior will be measured for individuals who were tested at the outlet. Untested clients are those who chose not to be tested and did not come with a test result from another facility. The major secondary outcome is the proportion of suspected malaria cases that are tested. This outcome will allow us to determine whether the conditional subsidy can drive demand for testing. Note that “untested people” here refers specifically to individuals that present at the shop without a referral but decline to be tested

people who were tested with an RDT

people who were tested with an RDT + # untested people who purchased an antimalarial

Other secondary outcomes will measure 1) adherence to the RDT result among all those tested at the outlet, 2) proportion of all suspected malaria cases that are managed appropriately (tested for malaria, and use ACT following a positive test or do not purchase an ACT after a negative test), and 3) ACT use by untested clients.

- Secondary outcome 2: Adherence to the RDT result among all those tested in the shop

people who tested positive and purchased ACT + # people tested negative and did not purchase any AM
people who were tested with an RDT

For those who are negative, if they buy any antimalarial (AM), including monotherapies and older therapies, they are not adhering to test result.

- Secondary outcome 3: Proportion of all suspected malaria cases that are managed appropriately in the shop

people who tested positive and purchased ACT + # people tested negative and did not purchase any AM
people who were tested with an RDT + # untested people who purchased an antimalarial

“Untested people” here refers specifically to individuals that present at the shop without a referral but decline to be tested

- Secondary outcome 4: ACT use among untested clients

people who were not tested in the shop and purchased an ACT
people who were not tested in the shop, did not have documentation of test and purchased any AM

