For the primary outcome, we include in both numerator and denominator those individuals who were referred from a health facility with a documented positive test result. That is, for the

primary outcome we are interested in evaluating the degree to which the interventions impacted the purchasing behavior of all suspected malaria cases seeking treatment. Our secondary outcomes do *not* include these individuals (i.e. the outcomes are calculated on the subset of individuals that present at the shop for testing without a referral). That is, for the secondary outcomes we are specifically interested in evaluating the degree to which the interventions impacted purchasing behavior among individuals who present at the shop for testing.

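### The exit-interview skips do not reliably capture outside tests and prescriptions, on which the primary numerator and, depending on the meaning of referral, the secondary denominators rely

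*Combined protocol and SAP*

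**What the plan says.** **Outcome definitions (section 6.1).** An ACT buyer is test-positive after a positive outlet test, or if the buyer "is referred from a health facility with a documented positive test result". On the untested group: "Untested clients are those who chose not to be tested and did not come with a test result from another facility". In the denominators for testing uptake and appropriate management, untested people are "individuals that present at the shop without a referral but decline to be tested". The last paragraph of 6.1 first describes the clients left out of the secondary outcomes as those with a documented positive from a health facility. It then restates the rule without that qualifier: "the outcomes are calculated on the subset of individuals that present at the shop for testing without a referral".

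**Routing (Appendix A.1, Sections 2 and 3).**
- Item 2.5, on treatment or care elsewhere: "If no or don't know, go to 3.1". This passes over 2.6 to 2.16.
- Item 2.8, on an outside malaria test: the no-test answer goes to 3.1, passing over 2.9 to 2.16.
- Item 2.12, on medicine already taken: "If 2 or 99, go to Section 3". A Yes is sent to 2.12, that is, to itself.
- Item 2.13: the interview stops if an antimalarial was taken.
- Item 2.14: "Did you come to the pharmacy today with a prescription from another provider/facility/lab".
- Item 3.2, put to everyone not tested in the shop: code 8 is a test elsewhere and code 9 is "Had a prescription for drug I needed before coming". It then leads to Section 4.

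**The concern.** The trial takes its outcomes from exit interviews, so a client's outside test or referral counts only if the form asks about it. Two groups can slip through.

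The first is clients who hold a documented positive but do not think of a laboratory or community-health-worker test as treatment or care. They may answer No at 2.5 and are then never asked about the test. If they buy an ACT without an outlet test, they stay in the primary denominator and drop out of the numerator.

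The second is clients who come with a prescription. The items meant for them sit behind four conditions that most such clients would not meet. If section 6.1 means to exclude every referred client from the secondary outcomes, some of these clients will be counted as untested walk-ins.

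Interviews carry no identifiers (sections 7 and 8), so an item that was not asked cannot be filled in later.

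**Working it through.** **1. Who is asked what.** This follows the printed skips. Where noted, the Yes exit at 2.12 is read as 2.13, which must be the intention.

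| Client | 2.8–2.10 asked? | 2.14–2.16 asked? | Other trace |
|---|---|---|---|
| Yes at 2.5, tested outside, no medicine yet | Yes | No | Test status already recorded |
| Yes at 2.5, tested outside, only non-antimalarial medicine taken | Yes | Only if the loop at 2.12 is read as 2.13 | Test status already recorded |
| Yes at 2.5, tested outside, antimalarial taken | Yes | No; stops at 2.13 on the same reading | Not applicable |
| Yes at 2.5, prescription but no outside test | 2.8 only | No | 2.7 code 5; 3.2 code 9 if not tested in the shop |
| No or Don't know at 2.5, tested outside, not tested in the shop | No | No | 3.2 code 8 or 9, without result or document |
| No or Don't know at 2.5, tested outside, tested again in the shop | No | No | None |

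So 2.14 is reached only with Yes at 2.5, an answer other than no test at 2.8, Yes at 2.12, and no antimalarial at 2.13. With the skips exactly as printed, no exit from 2.12 leads to 2.13–2.16 at all.

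**2. Primary outcome.** Section 6.2 expects 12% in Arm 1 and 35% in Arm 4. The difference is 35 − 12 = 23 points, as the plan states, and the ratio is 0.35/0.12 = 2.92. Section 6.4 will estimate both measures.

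Let h be the share of ACT buyers who hold a documented outside positive and q the share of those lost at 2.5. A lost client stays in the denominator, so the recorded proportion is p − h × q. The documents give neither h nor q; the values below are assumptions.

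| Assumption | Arm 1 | Arm 4 | Difference | Ratio |
|---|---|---|---|---|
| No loss | 12% | 35% | 23 | 2.92 |
| h = 2%, q = 10%, both arms | 12 − 0.2 = 11.8% | 35 − 0.2 = 34.8% | 23 | 2.95 |
| h = 10%, q = 50%, both arms | 12 − 5 = 7% | 35 − 5 = 30% | 23 | 4.29 |
| h = 10%, q = 50% in Arm 1; all such clients in Arm 4 retested positive at the outlet | 7% | 35% | 28 | 5.00 |
| q = 50%; h = 5% in Arm 1, 10% in Arm 4 | 12 − 2.5 = 9.5% | 30% | 20.5 | 3.16 |

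The last two rows show why loss could differ by arm. Only a test at the outlet earns the free ACT (section 3), so documented positives in Arms 3 and 4 have a reason to test again and would then be counted. Against that, if Arm 4 cuts ACT sales to untested and negative clients, documented positives become a larger share of its remaining buyers, and the same q costs that arm more.

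**3. Testing uptake, if referral includes a prescription without a test.** Uptake is T/(T + U), with T tested and U untested antimalarial buyers. If a share s of U should have been excluded, the intended value is T/(T + U(1 − s)). For an assumed recorded uptake of 30% (T = 30, U = 70):
- s = 5%: 30/96.5 = 31.1%
- s = 10%: 30/93 = 32.3%
- s = 20%: 30/86 = 34.9%

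If referral means only a documented positive test, these clients belong in U and there is no error.

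**The case against.** Four points weigh against making more of this.

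*The outside-test items come before the skip at 2.12.* A reader might infer that a typical referred client, tested at a clinic and not yet dosed, is lost. That does not follow. Such a client says Yes at 2.5 and is recorded at 2.8–2.10, so the test enters the primary outcome correctly. This stands in full.

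*No outcome formula uses a prescription.* If the final paragraph of 6.1 concerns only clients with a documented positive, someone with a prescription and no test is rightly counted as untested. This stands on that reading, but the same paragraph and the definition of untested people also use the term unqualified, so the text does not settle it.

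*There are back-ups.* A reader might infer that referral cannot be measured. That is too strong: 2.7 code 5 and 3.2 codes 8 and 9 catch part of it. But 2.7 lies behind 2.5, while 3.2 reaches only clients not tested in the shop and records neither result nor document.

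*A client referred from a health facility would naturally say Yes at 2.5.* Item 2.6 even lists private laboratories and community health workers among the follow-up answers, so the authors meant such visits to count. This suggests that the loss may be small. It does not remove it, because the respondent hears 2.5 before seeing that list. Whether a laboratory or community-health-worker result meets the health-facility wording of 6.1 is also left open, although 2.8 accepts any provider, facility or laboratory.

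**Conclusion.** The routing defect is certain, since it can be read off the form. Its effect on the results is not established. For the primary outcome, the possible loss is confined to clients who answer No or Don't know at 2.5, hold a documented positive, and buy an ACT without a positive outlet test. If that loss is equal across arms, it lowers the level and inflates the risk ratio but leaves the risk difference at 23 points. If it differs by arm, the difference can move either way. For the secondary outcomes, misclassification of prescription-only clients depends on how referral is read. A reader might infer that it must shrink the arm differences. That would require prescription holders not to take up testing, yet the free ACT in Arms 3 and 4 gives them a direct reason to test. Every magnitude above rests on assumed shares. The point is worth correcting because the repair is cheap and the missing answers cannot be recovered afterwards.

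**What to change.** - Ask 2.8–2.10 and 2.14–2.16 of every respondent. No or Don't know at 2.5 should pass over 2.6 and 2.7 only and go to 2.8.
- Route the no-test answer at 2.8 to 2.12, Yes at 2.12 to 2.13, and No or Don't know at 2.12 to 2.14.
- In section 6.1, define referral from these items. State whether a prescription without a test counts and which outside sources of a documented test qualify, then apply the definition to all secondary denominators.

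The cost is a set of skip-logic edits in the tablet form, a short definition in 6.1, and roughly a minute more per interview. No new items are needed. One side effect needs checking: more clients will reach the stop at 2.13, which covers antimalarials taken since the illness began, whereas the exclusion in section 4.2 uses a seven-day window. The two should be reconciled.
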